10.1.2 Reporting of serious adverse events (SAE) and other safety related events

As stated in the contract between the Clinic Arlesheim and Weleda AG, we will comply with our pharmacovigilance obligations. UAWs, SAEs and SUSARs will be reported to Weleda AG (see contact below) within a maximum of 24 hours. Any other side effects which are collected through the questionnaires will be notified to Weleda AG as soon as possible.

Address: WELEDA AG, [name]

Contact: [name], [contact], [contact]

Reporting of SAEs:

All SAEs must be reported immediately and within a maximum of $\underline{24 \text{ hours}}$ to the PI of the study. The PI will re-evaluate the SAE and make a causality assessment of the event to the study drug.

SAEs resulting in death are reported to the Ethics Committee via BASEC within 7 days.

If the possibility arises that a patient can admit the Clinic Arlesheim earlier than expected, it will lead to the discontinuation of this participant from the study. This hospital stay will not be considered as an SAE. Additionally, if a SAE is a clear result of the underlying disease, this SAE is exempted from expedited reporting.

Reporting of SUSARs

The Sponsor-Investigator needs to report SUSARs to the Ethics Committee via BASEC within 7 days, if the event is fatal, or within 15 days (all other events).

Reporting of Safety Signals

All suspected new risks and relevant new aspects of known adverse reactions that require safetyrelated measures, i.e. so called safety signals, must be reported to the Sponsor-Investigator within 24 hours. The Sponsor-Investigator must report the safety signals within 7 days to the Ethics Committee via BASEC.

Reporting and Handling of Pregnancies

Pregnant participants will be excluded from the clinical study

Periodic reporting of safety

An annual safety report is submitted once a year to the local Ethics Committee via PI.

10.1.3 Follow up of Serious Adverse Events

In case of participants terminating the study with reported ongoing SAEs beyond alert, participants will have a follow-up check-up as soon as the patient is hospitalized at the Clinic Arlesheim. The procedures depend on the type and severity of the SAE.

11. STATISTICAL METHODS

11.1 Hypothesis

Null hypothesis: There will be no difference in the primary outcome (LDQ score) between baseline and after four weeks of Amara treatment.

Alternative hypothesis: The LDQ score after four weeks treatment is different from the LDQ-score before the treatment.

In the case of statistical significance, the null hypothesis is rejected and the described difference (reduction or increase) is found to be proven according to the alternative hypothesis.

All secondary outcomes are purely exploratory, where effects are looked at and no Null Hypothesis is tested. This study is designed to get an idea of the effect size, since an estimation of the effect size is needed in order to calculate the sample size of a subsequent confirmatory study.

11.2 Determination of Sample Size

In this prospective open label study, placebo effects are likely to be present. Previous randomized controlled trials of therapy in functional gastrointestinal disorders indicate that this can be present in up to 40% of patients.(15) To compensate for this confounding factor and to demonstrate convincing

changes in perceived symptom burden at least 60% of patients should show improvement on-treatment compared to off-treatment (run-in phase). Assuming a moderate effect (Cohen's effect size of 0.4) on the primary outcome measure (effect size and standard deviation as in a previous paper by Carbone et al. (21)) power calculation suggests that 58 patients are required to detect a significant effect at a convincing level of statistical significance (beta 0.9, alpha <0.05). In the context of this study, the inclusion of 60 patients should also be sufficient to inform the design of any, future randomized, placebo-controlled study.

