Study Product / Intervention:	In this study the test medication (Amara drops) will be taken by the participants before meals. The herbal preparation is manufactured by Weleda AG, Arlesheim. Besides the bitter substances Artemisia absinthium, Cichorium intybus, Juniperus and Gentiana lutea, Amara Drops contain also Centaurium, Peucedanum, Achillea millefolia, Salvia officinalis and Taraxacum, all suspended in an alcohol-based tincture. The full indication text licensed by Swissmedic is: "According to the anthroposophical knowledge of man and nature, Weleda Amara-Drops can be used for digestive complaints such as heartburn, flatulence and bloating after meals, to stimulate the bile flow and for loss of appetite and nausea. The effect of Weleda Amara drops is based on a balanced mixture of medicinal plants with tonic (invigorating) and aromatic bitter substances, which are suitable for stimulating digestion. Weleda Amara drops mildly stimulate the secretion of saliva and gastric juices, promote the formation and secretion of bile and thus facilitate the digestion of fats. In addition, they are effective against flatulence and cramps."
Control Intervention:	No control group
Number of Participants with	Participants: 60 patients with functional dyspepsia with postprandial distress (Rome IV criteria).
Rationale:	There are no previous studies that have assessed the effect of Amara Drops in functional dyspepsia. Before randomized double blind controlled studies can be considered it is appropriate to assess perceived changes in symptom burden and physiological effects of Amara in clinical practice. At the same time the feasibility of recruiting this patient group and performing gastric emptying and other studies will be assessed. In this prospective open label study, placebo effects are likely to be present. Previous randomized controlled trials indicate that this can be up to 40%. To demonstrate convincing evidence of clinical efficacy a minimum 60% response rate above no treatment (run-in phase) must be demonstrated. Based on these considerations, for the primary outcome, power calculation suggests that at least 58 patients are required to detect moderate effects on perceived symptom burden at a convincing level of statistical significance (beta 0.9, alpha <0.01).
Study Duration:	2 years

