Study Schedule:	Month Year of First-Participant-In (planned): July 2022 Month Year of Last-Participant-In (planned): August 2024 Month Year of Last-Participant-Out (planned): September 2024
Investigator:	[name]. med. [name]
investigator.	Leitender Arzt, Zentrum für Integrative Gastroenterologie
	Leiter, Magen Darm Funktion: Basel, Labor und Klinik für funktionelle Magendarm Erkrankungen und Motilitätsstörungen
	[contact]
	[contact]
Study Centre:	Single Centre, Clinic Arlesheim (CLA), [name]

Statistical Considerations:	Differences between the scores from the primary and secondary outcome measurement variables – at baseline (following run-in) and after either 4- weeks treatment - will be compared initially by t-test if the data is normally distributed and Wilcoxon rank sum test when data are not normally distributed. In addition, we will perform univariate and multivariate linear regression analysis in which potential covariates will be considered; confounding will be evaluated by adding these variables to the linear regression model and looking at the change of the regression coefficients. These variables will include participants' gender, age, perceived symptom severity and gastric function at baseline.
	In the analysis of the primary outcome two-tailed $p \le 0.05$ will be considered statistically significant. Since the evaluation of the secondary endpoints is purely exploratory, other p-values will be calculated but reported without claiming significance,
GCP Statement:	This study will be conducted in compliance with the protocol, the current version of the Declaration of Helsinki, the ICH-GCP as well as all national legal and regulatory requirements.

ABBREVIATIONS

13C BT	¹³ C Acetate Breath Test
AE	Adverse Event
BASEC	Business Administration System for Ethical Committees, (https://submissions.swissethics.ch/en/)
CA	Competent Authority (e.g. Swissmedic)
CEC	Competent Ethics Committee
ClinO	Ordinance on Clinical Trials in Human Research (in German: KlinV)
CRF	Case Report Form
CTCAE	Common terminology criteria for adverse events
DSUR	Development safety update report
eCRF	Electronic Case Report Form
EKNZ	Ethikkommission Nordwest- und Zentralschweiz
HADS	Hospital Anxiety and Depression Scale
GCP	Good Clinical Practice
HRA	Federal Act on Research involving Human Beings (in German: HFG)
HRV	Heart Rate Variability
IB	Investigator's Brochure
IBS-SSS	Irritable Bowel Syndome Symptom Severity Score
ICS	Internal Coherence Scale

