3.8 Justification of choice of study population

Study participants will be recruited from patients referred to Gastroenterologists at Clinic Arlesheim for

assessment of dyspeptic symptoms. Investigations in this patient group identify an organic cause of these persistent symptoms in less than 1 in 4 cases.(16) Instead, functional dyspepsia is considered to be a disorder of brain-gut interaction, with symptoms related to both abnormal gastric motor function (e.g. delayed gastric emptying) and sensory function (peripheral hypersensitivity but also abnormal central processing).(1) Conservative measures (e.g. reduction in dietary fat) and medical treatment (e.g. acid suppression, prokinetics) often fail to improve symptoms.(5) Moreover, concerns about long-term side effects for certain medications (e.g. domperidone, metoclopramide),(20) and high rates of intolerance to prescription medications are reported.(5, 9) For these reasons, there is a clinical need for new and effective treatments of functional dyspepsia. Complementary and alternative medicines (CAM) based on natural products, such as plant-based "phytotherapy", are particularly appealing.(7, 9)

There are no previous studies that have assessed the effect of Amara Drops in functional dyspepsia. Before randomized double blind controlled studies can be considered prospective, open-label therapeutic study to assess perceived changes in symptom burden will be performed (at the same time the feasibility of recruiting this patient group and performing gastric emptying and other studies will be assessed). In this prospective open label study, placebo effects are likely to be present. Previous randomized controlled trials of therapy in functional gastrointestinal disorders indicate that this can be up to 40% in this group.(15) To compensate for this confounding factor and to demonstrate convincing changes in perceived symptom burden at least 60% of patients should show improvement on-treatment compared to off-treatment (run-in phase). Assuming a moderate effect (Cohen's effect size of 0.4) on the primary outcome measure (effect size and standard deviation as in a previous paper by Carbone et al. (21)) power calculation suggests that 58 patients are required to detect a significant effect at a convincing level of statistical significance (beta 0.9, alpha <0.01).

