7.4 Criteria for withdrawal / discontinuation of participants

In emergency situations, where acute symptoms develop or side effects are suspected to be associated with the Amara intake, treatment can be discontinued. The participation can also be terminated by the PI, by the Clinic Arlesheim or by the manufacturer of Amara if there is a suspicion of damage to health caused by the drug or a product defect, respectively. Also, as mentioned before, if there are any signs of patients unwilling to participate in the study it will result in the participant being excluded from the study.

If a participant does no longer fulfil the eligibility criteria at some point of the study, it will lead to the discontinuation of this participant from the study.

Participant recruitment will continue until 60 patients have completed the treatment arm of the study.

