11.5 Handling of missing data and drop-outs

Participants who filled out only the screening and/or only the first questionnaire (baseline) will be defined as dropouts. These dropouts will be replaced.

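### 58 patients is given as the 90%-power requirement at alpha 0.05 in section 11.2 and at alpha 0.01 in section 3.8 and the synopsis; it cannot be both

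*Protocol*

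**What the plan says.** Three places in the protocol give the sample size.

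- Section 11.2 assumes a Cohen's effect size of 0.4, with "effect size and standard deviation as in a previous paper", and concludes that "power calculation suggests that 58 patients are required to detect a significant effect at a convincing level of statistical significance (beta 0.9, alpha <0.05".
- Section 3.8 repeats that sentence with the same effect size, the same cited paper and the same 58, but ends "level of statistical significance (beta 0.9, alpha <0.01".
- The synopsis, under the number of participants, says at least 58 patients, describes the effects as moderate without a numerical effect size, and ends "convincing level of statistical significance (beta 0.9, alpha <0.01".

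The decision rule is the same in the synopsis (Statistical Considerations) and in section 11.4: "In the analysis of the primary outcome two-tailed" p-values up to 0.05 count as significant. The alternative hypothesis in section 11.1 is non-directional: "The LDQ score after four weeks treatment is different from the LDQ-score before the treatment". Section 7.4 sets the target: "Participant recruitment will continue until 60 patients have completed the treatment arm of the study". Section 11.5 says of dropouts: "These dropouts will be replaced". No dropout inflation is therefore needed to get from 58 to 60.

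**The concern.** The required number of patients depends on alpha. Two sentences that agree on effect size, power and N but differ fivefold in alpha cannot both be the output of one calculation, and nothing in the protocol explains the difference.

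What is at stake is the evidence standard that a reader believes the trial meets. It is a single-arm, open-label study, and section 6.1 says the placebo limitation is factored into the power calculation. The synopsis and section 3.8 present 0.01 as the level the study is powered for, while the analysis tests at 0.05.

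Two smaller faults sit in the same sentences. Beta is the type II error rate, so a beta of 0.9 read literally means 10% power; power 0.9 is clearly meant. The protocol also gives no SD value and does not say whether 0.4 is scaled by the SD of the score or by the SD of the within-patient change, so the 58 cannot be traced.

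**Working it through.** **Inputs.** Effect size 0.4, N = 58 and intended power 0.90 (sections 3.8 and 11.2); alpha 0.05 (11.2) or 0.01 (3.8, synopsis); two-tailed test at 0.05 (11.4); 60 completers (7.4). The comparison is before versus after in the same patients, so the tests are taken as paired. Section 11.4 names a rank sum test for non-normal data; the signed-rank form is used here because the data are paired.

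**Formulas.** Paired t-test: noncentral t with n − 1 degrees of freedom and noncentrality d√n, where d is mean change divided by SD of change. Signed-rank test: the same with n replaced by n × 3/π (normally distributed changes).

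**Step 1: can 58 be reproduced?** With d = 0.4 as the paired effect, the n needed for 90% power and the power at n = 58 are:

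| Alpha | n, t-test | n, signed-rank | Power at 58, t-test | Power at 58, signed-rank |
|---|---|---|---|---|
| 0.05 two-sided | 68 | 71 | 85.0% | 83.3% |
| 0.05 one-sided | 55 | 58 | 91.4% | 90.2% |
| 0.01 two-sided | 97 | 101 | 64.9% | 62.2% |
| 0.01 one-sided | 85 | 89 | 74.1% | 71.8% |

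Of these eight variants, only the one-sided 0.05 signed-rank calculation returns 58 (89.8% at n = 57). That this was the calculation used is an inference; the protocol does not say so, and it is not the planned two-tailed test. The responder figures in section 11.2 (40% placebo response, 60% target), treated as a one-sample proportion test with (z_α + z_β)² × 0.24 / 0.2², give 52 (one-sided 0.05), 64 (two-sided 0.05), 79 (one-sided 0.01) and 90 (two-sided 0.01), so they do not yield 58 either.

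**Step 2: the contradiction, without any assumption about d.** In the normal approximation N is proportional to (z_α + z_β)². At two-sided 0.05 this is (1.960 + 1.282)² = 10.51, and at two-sided 0.01 it is (2.576 + 1.282)² = 14.88. The ratio is 14.88 / 10.51 = 1.42, so the stricter level needs about 42% more patients whatever the effect size. With the exact paired t-test at n = 58:

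- If 58 is required at two-sided 0.05, the paired effect is 0.433. Power at 0.01 is then 73.4%, and 83 patients are needed.
- If 58 is required at two-sided 0.01, the paired effect is 0.522. Power at 0.05 is then 97.4%, and 41 patients are enough.

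**Step 3: the planned 60 completers, d = 0.4 as the paired effect.** At two-sided 0.05, power is 86.2% (t-test) or 84.5% (signed-rank). At two-sided 0.01 it is 66.8% or 64.2%. The effect detectable with 90% power at two-sided 0.05 is 0.425 (t-test) or 0.436 (signed-rank).

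**Step 4: if 0.4 is scaled by the SD of the score.** The paired effect is then 0.4 / √(2(1 − r)), where r is the correlation between the before and after scores. The protocol does not give r, so the values below are assumptions (t-test, n = 58, two-sided):

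| r | Paired effect | Power at 0.05 | Power at 0.01 |
|---|---|---|---|
| 0.3 | 0.338 | 71.6% | 47.0% |
| 0.5 | 0.400 | 85.0% | 64.9% |
| 0.7 | 0.516 | 97.2% | 89.3% |

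Power reaches 90% at r of about 0.57 for alpha 0.05 and at about 0.71 for alpha 0.01. No single r makes 58 the required number at both levels.

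**The case against.** A sample that is sufficient at 0.01 is also sufficient at 0.05, and the synopsis says at least 58. If 0.4 is scaled by the SD of the score and the before–after correlation is 0.71 or more, 58 gives 90% power or better at two-sided 0.01 (94.6% at r = 0.75). Both sentences would then be true as statements of sufficiency, and powering at a stricter level than the decision rule would be conservative. The shortfall figures depend on a reading of the effect size that only the cited paper could settle. The consequence is also small: the significance rule is clear and consistent, recruitment runs to 60 completers, and section 6.1 concedes that the design cannot evaluate efficacy.

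Part of this stands. The shortfall against 90% at the planned test is conditional on the scaling of 0.4, and neither the recruitment target nor the decision rule is affected. The sufficiency reading does not stand. Sections 3.8 and 11.2 say 58 patients are required, not that they suffice; if 58 were right at 0.01, 41 would be enough at 0.05. The reading also needs a correlation that the protocol never states.

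**Conclusion.** The concern holds. At least one of the two pairings of 58 with an alpha is wrong, whatever the effect size and its scaling. Section 11.2 agrees with the decision rule on 0.05, so the synopsis and section 3.8 claim a stricter level than the one tested.

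The size of the error depends on one unstated point. If 0.4 is the standardised paired change, the 90% claimed at 0.01 is about 65% (two-sided t-test, n = 58). At the planned two-sided 0.05 the shortfall is modest: 83% to 86% across both tests and n = 58 or 60. If 0.4 is scaled by the SD of the score, 58 may fall short of 90% or exceed it, depending on the correlation. The beta of 0.9 is a mislabel in all three places. This should be fixed, but it does not threaten the trial.

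**What to change.** 1. Go back to the original calculation and the cited paper. State the test, its sidedness, and the value and type of the SD (of the score or of the change) behind the 0.4.
2. Use two-sided alpha 0.05 in the synopsis, section 3.8 and section 11.2, to match section 11.4. If the recovered calculation was in fact run at 0.01, redo it at 0.05 rather than changing only the alpha beside the 58.
3. Replace beta 0.9 with power 0.9 (beta 0.1) in all three places.
4. Restate power for the 60 completers of section 7.4. If 0.4 is the paired-change effect, this is about 86% with the paired t-test or about 85% with the signed-rank test. Equivalently, 60 completers give 90% power for an effect of about 0.43 (t-test) or 0.44 (signed-rank).

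The cost is wording and restated figures, with no extra patients and no change to the target or the decision rule. If 0.4 is the paired-change effect, the stated power becomes slightly less favourable.

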11.3 Statistical criteria of termination of trial

Statistical criteria for the termination of the trial are not intended.

11.4 Planned Analyses

The statistic evaluation will be performed with SPSS (IBM SPSS Statistics, NY: IBM Corp.), version 26 or higher or Graphpad Prism (MacKiev Software), version 9.3.1 or higher or higher for PC or Mac. The demographic data will be analysed with descriptive statistics as average ± standard deviation (SD) for continuous variables and with percentage of total (%) for categorical variables.

Differences between the scores from the primary and secondary endpoint variables – at baseline and after 4-weeks treatment - will be compared initially by t-test if the data is normally distributed and Wilcoxon rank sum test when data are not normally distributed. In addition, if data is normally distributed we will perform univariate and multivariate linear regression analysis in which potential covariates will be considered; confounding will be evaluated by adding these variables to the linear regression model and looking at the change of the regression coefficients. These variables will include participants age, gender, symptom severity, psychological state and gastric function (sensitivity, emptying) at baseline.

In the analysis of the primary outcome two-tailed $p \le 0.05$ will be considered statistically significant. Since the evaluation of the secondary endpoints is purely exploratory, other p-values will be calculated but reported without claiming significance,

Data will be transferred from the REDCap software to the statistics program Prism for evaluation, where data are password protected and only accessible to the persons involved in the study.

All analyses will be performed at Klinik Arlesheim by the research group of [name]. [name], Department of Gastroenterology, Klinik Arlesheim.

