5. STUDY OUTCOMES

5.1 **Primary Outcome**

The primary outcome will be the perceived change of dyspeptic symptoms assessed by the Leuven Dyspepsia Questionnaire (LDQ) between visit 1 (off treatment) and 3 (after treatment). The questionnaire contains 3 domains/questions which related to: a) The inability to finish a meal due to early satiety b) The feeling of food lying heavily in the stomach c) Feeling bloated in the stomach. The questionnaire is presented to the patients in the form of three questions which define five grades of severity (0-4), and which are supported by pictograms expressing the associated severity. Higher total scores indicate more severe dyspeptic symptoms. For each subscale 0 normal, 1 mild dyspepsia; 2, moderate dyspepsia; 3, severe dyspepsia; 4, very severe dyspepsia. The questionnaire is to be evaluated on a daily basis and the mean of the values of the three symptoms is proposed to represent the severity of that day. A weekly score can be calculated from the daily scores and is currently proposed for the primary use of the scale.(21)

The LDQ has been developed using standard methods, including focus group interviews and cognitive debriefing interviews.(21) The further validation of the score was undertaken with the means of interventional studies, evaluating the response of this questionnaire to prokinetic and neuromodulatory medications. The LDQ has shown to be a good rating scale to be used as a severity indicator of dyspepsia and can be given to the same patient in subsequent sessions to track the change in symptoms. A minimally clinically important difference has also been determined. The results of this validation work have been published in peer reviewed journals.(22, 23)

The Leuven Postprandial Distress Scale, which is supported by the European Medicines Agency, is a sensitive and reliable patient-reported outcome instrument to assess symptoms in the functional dyspepsia/postprandial distress syndrome. Based on this information, the LDQ variable will be the main result to verify whether the test medication in this trial is efficacious. In this open-label study in which placebo and treatment effects are summed we expect a moderate to large >60% reduction in mean symptom burden as measured by the LDQ (results will be shown as mean \pm SD).

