- In addition to subjective patient related outcome measures, repeat ¹³C breath testing with the Nottingham Test Meal on and off treatment will provide physiological assessment of effects of Amara on gastric motor and sensory function. Continuous assessment of patient sensations during Drink tests (i.e., gastric filling) may be less impacted by patient recall than questionnaires. ¹³C breath testing provides an indirect assessment gastric emptying based on the excretion of ¹³CO₂ in the expired air. Although well validated against scintigraphy, it remains uncertain to what extent these results can be affected by individual patient factors other than gastric emptying (e.g. metabolism). Note that this limitation will not affect the results of this study because we will compare gastric emptying in patients on and off Amara treatment (i.e., patients act as their own control).
- Amara drops will be distributed for self-administration at home, thus, we rely on participants to report their intake accurately. Compliance will be checked as described above.
- The four-week duration of drug intake is relatively brief and may underestimate the treatment effect.
- This study may suffer from the limitation that participants will take other over the counter medications or engage in other treatments at home.
- This study design does not allow evaluating the efficacy of Amara medication. However, the aim of this prospective study is to acquire results on overall effectiveness that will inform the design of a randomized controlled study with this aim.

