6.2.3 Other methods of minimising bias

- Validated questionnaires will be used, and a statistical analysis plan is included in the protocol.
- Participants will record symptoms daily using a mobile application (paper version available). The study nurse will call participants if this technology is not used regularly.
- Objective assessment of gastric motor and sensory function will complement patient related outcome measurements.
- Compliance will be checked at the end of the treatment period.

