7.3 Assignment to study groups

The present trial is a single arm study.

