11.4.2 Primary Analysis

In the intention to treat analysis, all patients who have completed study questionnaires at baseline and after four-weeks of treatment will be included. Following covariates will be included in multivariate models: age, gender, dyspepsia symptom severity (LDQ), other gastrointestinal symptoms, psychological state and gastric function (sensitivity, emptying) at baseline.

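### The non-parametric test named for the baseline to week 4 comparison is the rank-sum test for independent samples, although both scores come from the same patients

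*Protocol*

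**What the plan says.** Section 11.4 (Planned Analyses) compares the primary and secondary scores at baseline and after four weeks by a t-test when the data are normal and otherwise by the "Wilcoxon rank sum test when data are not normally distributed". The synopsis, under statistical considerations, names the same test. Neither place says that the t-test is paired, and a signed-rank test is not mentioned anywhere.

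The rest of the protocol describes a within-patient comparison:

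- Section 7.3: "The present trial is a single arm study".
- Section 11.1, null hypothesis: "There will be no difference in the primary outcome (LDQ score) between baseline and after four weeks of Amara treatment".
- Section 11.4.2, primary analysis set: "all patients who have completed study questionnaires at baseline and after four-weeks of treatment will be included".
- Section 11.2, sample size: "power calculation suggests that 58 patients are required to detect a significant effect", at an effect size of 0.4.
- Section 6.1, limitations: "patients act as their own control". This is said of gastric emptying, a secondary outcome, but the design is the same for every outcome.

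Section 6.2.3 states that "a statistical analysis plan is included in the protocol", so section 11.4 is itself the stated plan for the test.

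**The concern.** The rank-sum test takes its null variance from two independent samples. Here each patient contributes one value to each sample. When a patient's two scores are positively correlated, the true variance of the difference is smaller than the test assumes. The test then rejects too seldom, both when there is no change and when there is one.

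The primary outcome is the only one tested for significance; section 11.4 makes no such claim for the secondary endpoints. What is at stake is therefore mainly that a real change in the Leuven score is missed, or that the test has to be switched after the data are seen.

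The non-normal branch may well be reached. Section 5.1 builds the score from three items graded 0 to 4, and section 7.1 admits only patients with at least 2 on at least two items, which cuts off the lower end of the baseline distribution.

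**Working it through.** **1. Is the comparison paired?** One arm (section 7.3), a before-and-after hypothesis (11.1) and an analysis set of patients with both questionnaires (11.4.2) leave no second independent group. Every comparison covered by section 11.4 is within patient.

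**2. Which calculation gives the stated 58?** Inputs from section 11.2: effect size d = 0.4, power 0.90 (printed as beta), alpha 0.05. Sidedness is not stated there; section 11.4 is two-tailed.

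- Paired, one-sided: n = ((1.645 + 1.282)/0.4)² = 53.5, so 54. The noncentral t gives 55. Allowing for signed-rank efficiency of 3/π = 0.955, 55/0.955 = 57.6, so **58**.
- Paired, two-sided: n = ((1.960 + 1.282)/0.4)² = 65.7, so 66. The noncentral t gives 68, and the signed-rank version 71.
- Two independent samples, per group: 2 × 53.5 = 107.0, so 108 one-sided; 2 × 65.7 = 131.3, so 132 two-sided.

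Only paired calculations come near 58, and the exact match is the one-sided signed-rank version.

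**3. Size of the effect, approximate formula.** Let ρ be the correlation between visits and d = 0.4 be measured on the SD of the change (an assumption; section 11.2 does not say). Ignoring the pairing overstates the standard error by 1/√(1 − ρ), so the effective critical value is 1.96/√(1 − ρ). With n = 60:

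- type I error ≈ 2[1 − Φ(1.96/√(1 − ρ))]
- power ≈ Φ(0.4·√(60 × 0.955) − 1.96/√(1 − ρ)) = Φ(3.03 − 1.96/√(1 − ρ))

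At ρ = 0.5 the critical value is 2.77. Type I error is then 0.6% and power Φ(0.26) = 60%.

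**4. Simulation** (bivariate normal, n = 60, 20,000 trials per scenario, two-sided 0.05). The correlations are assumed; the protocol gives none.

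| Correlation | Rank-sum power: formula | Rank-sum power: simulated | Signed-rank power | Paired t power | Rank-sum type I error |
|---|---|---|---|---|---|
| 0 | 86% | 85% | 84% | 86% | 5.0% |
| 0.3 | 75% | 74% | 84% | 86% | 1.9% |
| 0.5 | 60% | 59% | 84% | 86% | 0.6% |
| 0.7 | 29% | 30% | 84% | 86% | 0.06% |

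Signed-rank type I error stays at 4.7 to 5.1%. The fair comparator is the 84 to 86% that a correct paired test gives with 60 patients two-sided, not the stated 90%.

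**5. Bounded score.** This model is an illustration and its parameters are assumed. Three 0 to 4 items are cut from correlated latent normals at −1.2, −0.4, 0.4 and 1.2, with latent mean 0.5 and between-item correlation 0.7. The entry rule of section 7.1 applies at visit 1 (entry mean 8.6, SD 2.2). The shift is set to d = 0.4 or 0 on the SD of the change.

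| Score correlation | Rank-sum power | Signed-rank power | Rank-sum type I error |
|---|---|---|---|
| 0 | 78% | 83% | about 7% |
| 0.22 | 67% | 84% | 4.0% |
| 0.39 | 55% | 83% | 1.8% |
| 0.57 | 39% | 85% | 0.8% |
| 0.74 | 15% | 86% | below 0.1% |

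The row at zero shows that not all of this gap comes from the pairing. The entry rule truncates visit 1 only, so the two distributions differ in shape and spread (SD 2.2 against about 2.8 to 3.0), and equal means are then not the rank-sum null.

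**6. If 0.4 is on the SD of the raw score instead** (n = 58): rank-sum against signed-rank power is 56 v 70%, 56 v 83% and 60 v 97% at correlations 0.3, 0.5 and 0.7. The loss remains.

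**The case against.** The strongest reply is that this is a naming slip. The design, the hypothesis and the analysis set are all paired, and an analyst would probably run the right test. That is likely, and it limits the weight of the point. It does not remove it: the wrong test is named in both places, and the protocol presents itself as containing the analysis plan.

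The consequence is also conditional. It needs the non-normal branch to be taken and the named test to be run literally. This stands.

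The loss depends on the effect size as well. Section 5.1 expects a reduction of more than 60%, which on an entry mean of 8.6 is about 5.2 points (0.6 × 8.6), more than two baseline SDs. For effects that large the wrong test would still reject. At 0.6 SD of the change, rank-sum power is 98, 95 and 81% at correlations 0.3, 0.5 and 0.7, and at 0.8 it is about 99% or more. This stands too, but the trial is sized for 0.4, and that is where its power should be judged.

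Two further qualifications hold. The exact match to 58 needs a one-sided test although the primary test is two-tailed, so it supports a paired intention without proving it. And the statement that nothing is lost at zero correlation is true in the normal model but not in the bounded one; at a correlation of −0.2 the rank-sum type I error rises to about 7%.

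**Conclusion.** The concern holds. The plan names a test for independent samples for a comparison that is within patient throughout. If that branch is used as written and the visits are positively correlated, the primary test is in general conservative and underpowered at the design effect. Under the normal model, power falls from about 84% to 74, 59 or 30% at correlations of 0.3, 0.5 or 0.7. False positives are not inflated at the positive correlations examined.

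These figures rest on an assumed range of correlations, on 0.4 being measured on the SD of the change, and on the non-normal branch being taken. The error should be fixed. It is probably a slip of wording, and it matters mainly for the primary outcome because the secondary endpoints are exploratory.

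**What to change.** In section 11.4 and in the synopsis, replace the rank-sum test with the Wilcoxon signed-rank test and write paired t-test for t-test. State that the choice between them rests on the distribution of the within-patient differences, not on the scores at each visit. The same sentence then also covers the exploratory secondary endpoints.

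This is a wording correction in two places and costs no patients or data. Making it before the data are analysed avoids a switch of test that would later have to be justified as a deviation under section 11.4.6.
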